## **7.2 PARTICIPANT DISCONTINUATION/WITHDRAWAL FROM THE STUDY**

- A participant may withdraw from the study at any time at his/her own request, or may be withdrawn at any time at the discretion of the Investigator for safety, behavioral, or compliance reasons. This is expected to be uncommon.
- At the time of discontinuing from the study, if possible, an early discontinuation visit should be conducted, as shown in the SoA. See SoA ([Section 1.3](#)) for data to be collected at the time of study discontinuation and follow-up and for any further evaluations that need to be completed.
- If the participant withdraws consent for disclosure of future information, the Sponsor may retain and continue to use any data collected before such a withdrawal of consent.
- If a participant withdraws from the study, he/she may request destruction of any samples taken and not tested, and the Investigator must document this in the site study records.

The Investigators should discuss with study participants key visits to attend. The value of all their study data collected during their continued involvement will be emphasized as important to the public health value of the study.

Participants who withdraw from the study intervention should be explicitly asked about the contribution of possible AEs to their decision, and any AE information elicited must be documented.

All study withdrawals should be recorded by the Investigator in the appropriate pages of the eCRF and in the participant's medical records. In the medical record, at least the date of the withdrawal and the reason should be documented.

In addition, a participant may withdraw his/her consent to stop participating in the study. Withdrawal of consent for study intervention should be distinguished from withdrawal of consent for follow-up visits and from withdrawal of consent for nonparticipant contact follow-up, eg, medical record checks. The site should document any case of withdrawal of consent.

Participants who have withdrawn from the study cannot be rerandomized (treated) in the study. Their inclusion and intervention numbers must not be reused.

## **7.3 STUDY LEVEL STOPPING CRITERIA**

The study may be stopped if any of the following criteria are met:

- Cancellation of or change in the drug development program per the discretion of the Sponsor.
- Emergence of AEs unknown to date or increased frequency and/or severity and/or a duration of known AEs that makes the benefit-risk for study continuation negative.

- The results of the interim data review meet no-go criteria as detailed in the Statistical Analysis Plan (SAP).
- Participant enrollment (evaluated after a reasonable amount of time) is unsatisfactory.

#### **7.4 LOST TO FOLLOW UP**

A participant will be considered lost to follow-up if he/she repeatedly fails to return for scheduled visits and is unable to be contacted by the study site.

The following actions must be taken if a participant fails to return to the site for a required study visit:

- The site must attempt to contact the participant and reschedule the missed visit as soon as possible and counsel the participant on the importance of maintaining the assigned visit schedule and ascertain whether or not the participant wishes to and/or should continue in the study.
- Before a participant is deemed lost to follow up, the Investigator or designee must make every effort to regain contact with the participant (where possible, 3 telephone calls and, if necessary, a certified letter to the participant's last known mailing address or local equivalent methods). These contact attempts should be documented in the participant's medical record.
- Should the participant continue to be unreachable, he/she will be considered to have withdrawn from the study.
- Site personnel, or an independent third party, will attempt to collect the vital status of the participant within legal and ethical boundaries for all participants randomized, including those who did not get study intervention. Public sources may be searched for vital status information. If vital status is determined as deceased, this will be documented and the participant will not be considered lost to follow-up. Sponsor personnel will not be involved in any attempts to collect vital status information.

Discontinuation of specific sites or of the study as a whole are handled as part of Appendix 1 (Section 10.1).

## 8 STUDY ASSESSMENTS AND PROCEDURES

- Study procedures and their timing are summarized in the SoA ([Section 1.3](#)). Protocol waivers or exemptions are not allowed.
- Adherence to the study design requirements, including those specified in the SoA, is essential and required for study conduct.
- All screening evaluations must be completed and reviewed to confirm that potential participants meet all eligibility criteria. The Investigator will maintain a screening log to record details of all participants screened and to confirm eligibility or record reasons for screening failure, as applicable.
- Procedures conducted as part of the participant's routine clinical management (eg, blood count, urine tests) and obtained before signing of the ICF may be utilized for screening or baseline purposes provided the procedures met the protocol-specified criteria and were performed within the time frame defined in the SoA.
  - Repeat or unscheduled samples may be taken for safety reasons or for technical issues with the samples.
  - If onsite visits are not feasible (due to ALS progression, increased monitoring for AE follow-up), remote visits (eg, with home nurses, a home health vendor, a local clinic etc.) may be planned for the collection of safety and/or efficacy data.

For a regional or national emergency declared by a governmental agency, contingency measures are included in Appendix 9 ([Section 10.9](#)).

### 8.1 EFFICACY ASSESSMENTS

Planned time points for all efficacy assessments are provided in the SoA ([Section 1.3](#)).

Key efficacy assessments will be measured by trained Investigator or rater. Same Investigator or rater is preferred to conduct the same assessment for individual participant at each visit, if possible.

#### 8.1.1 ALSFRS-R

The ALSFRS-R is composed of 12 items across 4 subdomains of bodily function (bulbar, fine motor, gross motor, and breathing), with each item scored on an ordinal scale from 0 (total loss of function) to 4 (no loss of function). The total score of the ALSFRS-R ranges from 0 to 48, with a higher score indicating better function ([23](#)). Good reliability between face-to-face and telephone administration of the ALSFRS-R has been demonstrated ([24](#)).

#### 8.1.2 Slow vital capacity (SVC)

SVC is measured in participants while they are in an upright position at least 3 trials per assessment or up to 5 trials when the highest and second highest of the first 3 measurements differ by 10% or more. SVC volumes are standardized to the percentage of the predicted normal value based on age, sex, and height ([25](#)). The highest SVC score among all attempts will be used for analysis.

### **8.1.3 Muscle strength measurement**

The muscles measured in the study include upper-limb and lower-limb muscle groups. Bilateral hand grip will be measured using a grip dynamometer and all other muscles included in this study will be measured using a handheld dynamometer. For each muscle to be tested, 2 trials will be performed. If the variability of the 2 trials is 15% or less, values from both trials will be recorded and the higher score will be used for analysis. If the variability is greater than 15%, a 3 trial will be performed, all the values will be recorded and the maximum value of the 3 trials will be accepted. The order of muscle testing is standardized (26).

### **8.1.4 ALSAQ-5**

The ALSAQ-5 is a PRO that consists of 5 items derived from the ALSAQ-40. The 5 items closely resemble those of the 5-dimension scores of the ALSAQ-40: eating and drinking; communication; activities of daily living/independence; physical mobility; and emotional functioning. The ALSAQ-5 has a recall period of the past 2 weeks and takes approximately 5 minutes to complete. Each item is scored on a 5-point Likert scale ranging from 0 (never) to 4 (always or cannot do at all) according to the frequency of a particular problem. Total scores range from 0 to 20, with higher scores indicative of greater physical and emotional limitations.

### **8.1.6 Survival**

The survival endpoint will be defined as the time to death or permanent assisted ventilation (>22 hours a day for >7 consecutive days), whichever comes first. The CAFS is a combined endpoint that evaluates function and survival together to provide a more accurate indication of a treatment effect than independent analyses. Results from the ALSFRS-R and survival data will be used together to generate the CAFS scale.

Topic	Percentage
Smart cities	98
Smart homes	98
Smart grids	98
Smart transportation	98
Smart agriculture	98
Smart energy	98
Smart waste management	98
Smart water management	98
Smart healthcare	98
Smart manufacturing	98
Smart retail	98
Smart government services	98
The concept of a 'smart city'	60

## 8.2 SAFETY ASSESSMENTS

This section presents safety assessments other than AEs, which are presented in [Section 8.3](#).

Planned time points for all safety assessments are provided in the SoA.

### 8.2.1 Physical examinations

- A complete physical examination will include, at a minimum, assessments of the cardiovascular, respiratory, gastrointestinal, neurological systems, skin and lymph node area systems. Height and weight will also be measured and recorded.
- A brief physical examination will include, at a minimum, assessments of the skin, lymph node areas, lungs, cardiovascular system, and abdomen (liver and spleen).
- Investigators should pay special attention to clinical signs related to previous serious illnesses.

### **8.2.2 Neurological examinations**

- A neurological examination will be performed and the results recorded. A complete neurological examination will include, at a minimum, assessments of mental status, cranial nerves, motor and sensory function, reflexes, coordination, and stance/gait.
- A brief neurological examination will include, at a minimum, assessments of assessments of cranial nerves, coordination/cerebellar function, reflexes, and motor function.
- Investigators should pay special attention to clinical signs related to previous neurological illnesses, including ALS.

### **8.2.3 Vital signs**

- Oral, tympanic, axillary, or skin temperature, heart rate, respiratory rate, and blood pressure will be assessed.
- Blood pressure and pulse measurements will be assessed with a completely automated device. Manual techniques will be used only if an automated device is not available.
- Blood pressure and pulse measurements should be preceded by at least 5 minutes of rest for the participant in a quiet setting without distractions (eg, television, cell phones).
- Vital signs (usually should be taken before blood collection for laboratory tests) will consist of 1 pulse and 3 blood pressure measurements (3 consecutive sitting blood pressure readings will be recorded at intervals of at least 1 minute). The average of the 3 blood pressure readings will be recorded. At Day 1 visit, postdose vital signs should be measured at least 10 minutes after the second PK sample collection (recommended to be measured within 10 to 30 minutes after the second PK sample collection).

### **8.2.4 Electrocardiograms**

- Single 12-lead ECG will be obtained as outlined in the SoA (see [Section 1.3](#)) using an ECG machine that automatically calculates the heart rate and measures PR, QRS, QT, and QTc intervals.
- In case the ECG machine does not automatically calculate QTcF, manual calculation using following formula ( $QTcF=QT/RR1/3$ ) or automatic website calculator (eg, <https://reference.medscape.com/calculator/48/ecg-corrected-qt>) is acceptable.
- ECGs and (longer) rhythm strips will be obtained locally.
- If a clinically significant finding is identified in the ECG (including, but not limited to changes from baseline in QTcF after enrollment), the Investigator or delegate will determine if the participant can continue in the study and if any change in participant management is needed including but not limited to referral to cardiology, and/or Holter monitor. The Investigator or delegate should perform the following tasks:
  - Review the ECG in a timely manner
  - Document the interpretation, sign and date it on ECG printout
  - Record your (or appropriate qualified physician) medical opinion (“normal” or “abnormal”) on the study participant’s records and in the eCRF
  - Assess for any symptoms of cardiac issues

- Each time when it is medically needed for clinical management of the study participant or/and in case of any safety concerns, additional ECG should be performed, and findings reported in the eCRF dedicated unscheduled visits ECG forms
- Clinically significant findings are to be checked with pre-existing medical history or/and, if appropriate, consider AE.

Please refer to (27) and (28) for definitions of heart failures classification.

#### **8.2.5 Clinical safety laboratory assessments**

- See Appendix 2 ([Section 10.2](#)) for the list of clinical laboratory tests to be performed and to the SoA ([Section 1.3](#)) for the timing and frequency.
- The Investigator must review the laboratory report, document this review, and record any clinically significant changes occurring during the study as an AE. The laboratory reports must be filed with the source documents. Abnormal laboratory findings associated with the underlying disease are not considered clinically significant, unless judged by the Investigator to be more severe than expected for the participant's condition.
- All abnormal laboratory values that are considered by the Investigator as clinically significant during participation in the study or within 2 weeks after the last dose of study intervention should be repeated until the values return to normal or baseline or are no longer considered clinically significant by the Investigator.
  - If clinically significant values do not return to normal/baseline within a period of time judged reasonable by the Investigator, the etiology should be identified and the Sponsor notified.
  - All protocol-required laboratory tests, as defined in Appendix 2 ([Section 10.2](#)), must be conducted in accordance with the laboratory manual and the SoA ([Section 1.3](#)).
  - If laboratory values from nonprotocol-specified laboratory tests performed at the institution's local laboratory require a change in participant management or are considered clinically significant by the Investigator (eg, SAE or AE or dose modification), then the results must be recorded.

#### **8.2.6 Pregnancy testing**

For female participants of childbearing potential, a pregnancy test will be performed at each onsite visit during the whole study period. Additionally, monthly urine pregnancy tests will be provided directly to participants and self-conducted by them at home when not coinciding with a clinic visit. The study site staff will call the participants to remind them to conduct the monthly pregnancy tests and collect the results. A serum pregnancy test will be conducted at the screening visit, the last follow-up visit at Week 106, and the early discontinuation visit, and a urine pregnancy test will be performed for all other visits.

#### **8.2.7 Suicidal ideation and behavior (SIB) risk monitoring**

SAR443820 crosses the blood-brain barrier. Assessment of suicidal ideation and behavior/treatment-emergent suicidal ideation and behavior will be monitored during ACT16970

using the C-SSRS. For safety reasons, the C-SSRS will be administered throughout the study by the Investigator or delegated to an individual who is certified to administer the scale.

Study intervention administration must be interrupted if a participant scores “yes” on items 4 or 5 of the Suicidal Ideation Section of the C-SSRS or “yes” on any item of the Suicidal Behavior Section. A mental health professional will be consulted and will decide whether the study intervention can be restarted and if any additional risk mitigation strategies are required (eg, increased monitoring, antidepressant administration).

Participants being treated with the study intervention should be monitored appropriately and observed closely for suicidal ideation and behavior or any other unusual changes in behavior. Especially at the beginning and end of the course of treatment, consideration should be given to discontinuing the study medication in participants who experience signs of suicidal ideation or behavior following a risk assessment.

### **8.3 ADVERSE EVENTS (AES), SERIOUS ADVERSE EVENTS (SAES) AND OTHER SAFETY REPORTING**

The definitions of AEs and SAEs can be found in Appendix 3 ([Section 10.3](#)). The definition of AESI is provided in [Section 8.3.8](#).

AEs will be reported by the participant (or, when appropriate, by a caregiver, surrogate, or the participant’s legally authorized representative).

The Investigator and any qualified designees are responsible for detecting, documenting, and recording events that meet the definition of an AE or SAE and remain responsible for following up AEs that are serious, considered related to the study intervention or study procedures, or that caused the participant to discontinue the study intervention (see [Section 7](#)).

The method of recording, evaluating, and assessing causality of AEs and SAEs and the procedures for completing and transmitting SAE reports are provided in Appendix 3 ([Section 10.3](#)).

#### **8.3.1 Time period and frequency for collecting AE and SAE information**

All AEs (serious or nonserious) will be collected from the signing of the ICF until the follow-up visit at the time points specified in the SoA ([Section 1.3](#)).

All SAEs and AESI will be recorded and reported to the Sponsor or designee immediately and under no circumstance should this exceed 24 hours, as indicated in Appendix 3 ([Section 10.3](#)). The Investigator will submit any updated SAE data to the Sponsor within 24 hours of it being available.

Investigators are not obligated to actively seek information on AEs or SAEs after conclusion of the study participation. However, if the Investigator learns of any SAE, including a death, at any time after a participant has been discharged from the study, and he/she considers the event to be reasonably related to the study intervention or study participation, the Investigator must promptly notify the Sponsor.

### **8.3.2 Method of detecting AEs and SAEs**

Care will be taken not to introduce bias when detecting AEs and/or SAEs. Open-ended and non-leading verbal questioning of the participant is the preferred method to inquire about AE occurrences.

### **8.3.3 Follow-up of AEs and SAEs**

After the initial AE/AESI/SAE report, the Investigator is required to proactively follow each participant at subsequent visits/contacts. At the prespecified study end-date, all SAEs will be followed until resolution, stabilization, the event is otherwise explained, or the participant is lost to follow-up (as defined in [Section 7.4](#)). Further information on follow-up procedures is provided in Appendix 3 ([Section 10.3](#)).

### **8.3.4 Regulatory reporting requirements for SAEs**

- Prompt notification by the Investigator to the Sponsor of an SAE is essential so that legal obligations and ethical responsibilities towards the safety of participants and the safety of a study intervention under clinical investigation are met.
- The Sponsor has a legal responsibility to notify both the local regulatory authority and other regulatory agencies about the safety of a study intervention under clinical investigation. The Sponsor will comply with country-specific regulatory requirements relating to safety reporting to the regulatory authority, IRB/Independent Ethics Committee (IEC), and Investigators.
- Serious adverse events that are considered expected will be specified in IB.
- Investigator safety reports must be prepared for SUSARs according to local regulatory requirements and Sponsor policy and forwarded to Investigators as necessary.
- An Investigator who receives an Investigator safety report describing an SAE, SUSAR or any other specific safety information (eg, summary or listing of SAEs) from the Sponsor will review and then file it along with the IB and will notify the IRB/IEC, if appropriate according to local requirements. It is the responsibility of the Sponsor to assess whether an event meets the criteria for a SUSAR, and therefore, is expedited to regulatory authorities.

### **8.3.5 Pregnancy**

- Details of all pregnancies in female participants and female partners of male participants will be collected after the start of study intervention and until the time period for postintervention contraception determined in [Section 5.1](#).
- If a pregnancy is reported, the Investigator will record pregnancy information on the appropriate form and submit it to the Sponsor within 24 hours of learning of the pregnancy of a female participant or female partner of male participant after obtaining the necessary signed informed consent from the female partner.
- Abnormal pregnancy outcomes (eg, spontaneous abortion, fetal death, stillbirth, congenital anomalies, ectopic pregnancy) are considered SAEs and will be reported as such.

- The participant or female partner of a male participant will be followed to determine the outcome of the pregnancy. The Investigator will collect follow-up information on the participant or female partner of a male participant and the neonate, and the information will be forwarded to the Sponsor.
- Any poststudy pregnancy-related SAE considered reasonably related to the study intervention by the Investigator will be reported to the Sponsor as described in [Section 8.3.4](#). While the Investigator is not obligated to actively seek this information in former study participants, he or she may learn of an SAE through spontaneous reporting.
- Any female participant who becomes pregnant while participating in the study will discontinue study intervention.

### **8.3.6 Cardiovascular and death events**

Since the risk of cardiovascular events is low based on preclinical and Phase 1 study results, cardiovascular events are not AESIs and will be reported per standard safety reporting and safety oversight practices (including a data review by the data monitoring committee [DMC]).

Death events will be reported per standard SAE reporting rules. Every effort will be made to clarify the cause of death and to report the diagnosis of a fatal event, except ALS, as an SAE.

### **8.3.7 Disease-related events and/or disease-related outcomes not qualifying as AEs or SAEs**

Respiratory function decline is a type of disease-related event (DRE). DREs are common in participants with ALS and can be serious/life threatening.

Because a decline in respiratory function, including respiratory failure, is typically associated with ALS, it will not be reported according to the standard process for expedited reporting of SAEs even though the event may meet the definition of an SAE. These events will be recorded within the eCRF. These DREs will be monitored by an independent DMC on a routine basis (See [Section 10.1](#)). Disease progression-related measures will not be recorded as AEs/SAsE, including ALSFRS-R, vital capacity results, and muscle strength results. Additionally, the scheduled events, eg, hospitalization for an elective procedure, including G-tube placement, are not considered SAEs since an elective or scheduled “procedure” or a “treatment” are not an untoward medical occurrence.

NOTE: However, if either of the following conditions applies, then the events must be recorded and reported as an AE/SAE (instead of a DRE):

- The event is, in the Investigator’s opinion, of greater intensity, frequency, or duration than expected for the individual participant.

OR

- The Investigator considers that there is a reasonable possibility that the event was related to study intervention.

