## 2.2 BACKGROUND

ALS is a fatal neurodegenerative disorder characterized by progressive loss of motor neurons in the cortex, brain stem, and spinal cord. Relentless and progressive muscle atrophy and weakness are hallmarks of ALS. Most patients with ALS die from respiratory failure within 3 to 5 years after disease onset. Among the 3 Food and Drug Administration (FDA)-approved ALS treatments, riluzole and edaravone demonstrate only a moderate effect either on survival or functional decline, respectively, and more data is needed to further support the treatment effect of the recently approved treatment, the combination of sodium phenylbutyrate and taurursodiol. Therefore, there is still a significant unmet medical need for treating individuals with ALS.

SAR443820 has demonstrated strong RIPK1 inhibition with high potency in vitro in various cell types. Refer to the SAR443820 Investigator's Brochure (IB) for a detailed description of the chemistry, pharmacology, efficacy, and safety of SAR443820.

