- Any treatment-emergent AESI
- Any TEAE considered by the investigator as related to IMP

An additional overview summary including the number and rate of events will be provided.

The AE summaries of [Table 5](#) will be generated with number (%) of participants experiencing at least one event.

Listings of SAEs from randomized participants, AEs from participants who are treated but not randomized, AEs leading to treatment/study discontinuation and severe AEs will be provided.

Table 5 - Analyses of adverse events

Type of AE	MedDRA levels
All TEAEs	Primary SOC and PT
Common TEAE ($\geq 2\%$ in any group)	PT
TEAEs related to IMP as per Investigator's judgment	Primary SOC and PT
TEAE by maximal intensity	PT
Treatment emergent SAEs	Primary SOC and PT
Treatment emergent SAEs related to IMP as per Investigator's judgment	Primary SOC and PT
Treatment emergent AESIs	AESI category and PT
TEAEs leading to permanent intervention discontinuation	Primary SOC and PT
TEAEs leading to death ^b	Primary SOC and PT
Pretreatment AEs	Overview ^a
Post-treatment AEs	Primary SOC and PT
	Overview ^a
	Primary SOC and PT

^a Will include the following AE categories: any AEs, any serious AEs, any AEs leading to death, any AEs leading to permanent intervention discontinuation

^b Death as an outcome of the AE as reported by the Investigator in the AE page

Analysis of deaths in Part A and Part A + Part B

In addition to the analyses of deaths included in [Table 5](#), the number (%) of participants in the following categories will be provided:

- Deaths during the treatment-emergent period and post-treatment period
- Deaths in non-randomized participants or randomized but not treated participants

Analysis of adverse events of special interest (AESIs) in Part A and Part A + Part B

Adverse events of special interest (AESIs) will be selected for analyses as indicated in [Table 6](#). Number (%) of participants experiencing at least one event will be provided for each event of interest. Tables will be sorted as indicated in [Table 4](#). A listing of AESIs will also be provided.

Table 6 - Selections for AESIs

AESIs	Selection
Pregnancy of a female participant or female partner of a male participant	Dedicated CRF page (AECAT="PREGNANCY DATA")
Symptomatic overdose (serious or non-serious) with IMP	Dedicated CRF page (AECAT="OVERDOSE DATA"; must be symptomatic and AESI marked "Y")
Convulsions	CMQsn00079 for selection and AESI marked "Y"

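### Respiratory failure judged expected and unrelated is recorded as a disease-related event, but the SAP plans no summary of these events by arm

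*Protocol*

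**What the plan says.** Protocol 2.2 states: "Most patients with ALS die from respiratory failure within 3 to 5 years after disease onset". Protocol 8.3.7 then treats respiratory decline, respiratory failure included, as a DRE. It says of such a decline that "it will not be reported according to the standard process for expedited reporting of SAEs", and it acknowledges that the event could still satisfy the SAE definition. On collection and oversight it says "These events will be recorded within the eCRF" and "These DREs will be monitored by an independent DMC on a routine basis".

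There is an exception. If the event is, in the investigator's view, "of greater intensity, frequency, or duration than expected for the individual participant", or if a relation to study intervention is reasonably possible, "then the events must be recorded and reported as an AE/SAE (instead of a DRE". Protocol 10.3.1 agrees with this: expected progression of the disease under study is not an AE.

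For deaths, Protocol 8.3.6 applies the SAE rules and asks sites "to report the diagnosis of a fatal event, except ALS, as an SAE".

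SAP 3.6.2 summarises TEAEs, SAEs, AESIs and deaths. The fatal-TEAE row of SAP Table 5 is defined as "Death as an outcome of the AE as reported by the Investigator in the AE page". A separate count gives deaths by period. SAP 3.6.3 adds laboratory, vital-sign, ECG, liver-injury and C-SSRS summaries. DREs are named neither there nor in Protocol 9.4.6.

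**The concern.** Safety and tolerability against placebo is a Part A secondary objective, with SAE and TEAE incidence among its endpoints. Respiratory failure is, by the protocol's own account, how most people with ALS die.

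The exception in 8.3.7 works one participant at a time. If a drug made an expected complication more frequent, each extra case could still look expected to a blinded investigator and be filed as a DRE. An excess of that kind shows only when counts are compared between randomised arms. The plan collects the events but does not schedule that comparison for the study report.

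**Working it through.** The documents state no figure to reproduce, so the check traces each kind of respiratory event from the protocol's reporting route to the SAP's outputs.

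| Respiratory event | Route in the protocol | Planned output by arm |
|---|---|---|
| Worse than expected, or possibly related | AE/SAE (8.3.7 exception) | SAP Table 5 |
| Expected and unrelated, fatal | DRE under 8.3.7; death under 8.3.6 | Death count by period (SAP 3.6.2); time to death (SAP 3.3.1.2). In the fatal-TEAE row only if the site completed an AE page |
| Expected and unrelated, non-fatal, reaching permanent assisted ventilation | DRE | Time to death or permanent ventilation (SAP 3.3.1.2) |
| Expected and unrelated, non-fatal, short of permanent ventilation | DRE | None in the readable text |

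The last row is the gap. The other analyses that touch on breathing were checked against it:

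- **SVC (SAP 3.3.1.2).** This is a mean change from an MMRM, with missing values assumed missing at random. It is not an event incidence. In Part B, footnote e of the schedule leaves SVC off the assessments kept after early IMP discontinuation.
- **ALSFRS-R.** It has a breathing subdomain and can be taken by telephone, but the analysis is of the mean total score.
- **Time to death or permanent ventilation.** The clock starts at randomisation, so the placebo-controlled weeks are covered, and Kaplan-Meier proportions are planned at time points that include Week 24. The ventilation component needs more than 22 hours a day for more than 7 consecutive days, so lesser respiratory failure does not count.
- **CAFS.** Protocol 8.1.6 and SAP 3.2.1 define survival as death or permanent ventilation, while the pairwise rule in SAP 3.2.1 speaks only of dying. On either reading, lesser respiratory failure is not counted as an event.
- **Population.** These efficacy analyses use the ITT or mITT population; Part A safety is by treatment actually received (SAP 3.6).

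**What a DRE table could show.** This uses the planned arms of 87 and 174 (Protocol 4.1) and assumed incidences, since the documents give none. For placebo incidence p0 and SAR443820 incidence p1:

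- pooled p = (87·p0 + 174·p1)/261
- SE0 = √[p(1−p)(1/87 + 1/174)]
- SE1 = √[p0(1−p0)/87 + p1(1−p1)/174]
- power = Φ[(p1 − p0 − 1.96·SE0)/SE1]

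For 5% v 10%: p = 0.0833, SE0 = 0.0363, SE1 = 0.0326, (0.05 − 0.0711)/0.0326 = −0.65, power about 26%. The same formula gives about 16% for 3% v 6% and 54% for 10% v 20%. A DRE table would therefore be descriptive, which matches the SAP's rule of no testing for safety. These figures say nothing about whether an excess exists.

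**The case against.** The strongest reply is that the plan already covers most of this. Events worse than expected or possibly related are AEs or SAEs. Deaths are counted by period however they are coded. Death or permanent ventilation is compared by randomised arm, SVC is in the testing hierarchy, and the DMC sees DREs routinely. All of that stands, and it narrows the gap to the last row of the table above. It does not close it: none of these outputs gives the incidence of lesser respiratory failure by arm, and DMC review does not put a comparison in the report.

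A second reply is that 8.3.7 waives only expedited reporting, so the events remain AEs. The operative sentence allows that reading. The section heading, the wording of the exception and Protocol 10.3.1 all point to separate routes. If the sponsor meant the narrower reading, the SAP should say that Table 5 includes these events.

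A third reply is that tertiary endpoints are redacted and SAP 3.4.1 is not shown, so some respiratory events may be analysed there. That stands as a limit on the finding.

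A reader might also infer more than the documents support:

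- **That the SAP tabulates AEs only, or that respiratory failure reaches no safety table.** Deaths, laboratory values, vital signs, ECG and C-SSRS are all planned, and excepted events enter Table 5.
- **That most serious respiratory events are lost.** Serious infections remain AESIs with their own row in SAP Table 6, exclusion criterion E 04 gives pneumonia as an example of a serious infection, and no document figure supports a share.
- **That CAFS ignores ventilation.** The text is ambiguous.
- **That 8.3.6 and 8.3.7 contradict each other.** They can be read together, with expected respiratory failure as part of ALS. Sites may still sort fatal cases differently, which would move the AE-based fatal row and not the separate death count.

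**Conclusion.** The point holds in a limited form. Respiratory decline or failure judged expected and unrelated is collected and reviewed by the DMC, but the readable SAP 3.6 plans no table or listing of it by arm. Non-fatal cases short of permanent assisted ventilation have no planned incidence comparison, and the SAE incidence can omit events that meet an SAE criterion.

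No size can be given. The documents state no rate of respiratory failure over 24 weeks, and how many cases investigators would move to AE/SAE reporting is unknown. The conclusion assumes that DREs are filed separately from AEs, as the heading and exception in 8.3.7 indicate, and that no redacted output already tabulates them. The primary analysis and the testing hierarchy are unaffected.

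**What to change.** In SAP 3.6.2, before the Part A database lock, add:

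- A descriptive table of DREs by actual treatment group, for Part A and for Part A + Part B, giving number and percentage of participants with any DRE, and with a fatal or serious DRE where the eCRF captures this.
- A matching listing.
- One row combining SAEs with DREs that meet an SAE criterion, built from both sources, so that the result does not depend on how sites sort events between Protocol 8.3.6 and 8.3.7.

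No testing is needed, and site reporting rules do not change. The eCRF is not among the documents. If it does not record seriousness for DREs, the SAP should say so, and the any-event row and the listing then carry the information.

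The cost is one or two extra tables from recorded events. The combined row will be higher than the SAE row wherever serious DREs occur, and needs a sentence of explanation.
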